9.9 Timing of Analysis

Reviews of safety, PK, and clinical efficacy data will be performed as specified in Section 4.1.

The primary analysis will be conducted following completion of the DB Intervention Period.

The final analysis will be conducted at the end of the LTE; results will be presented in a final clinical study report.

9.10 Sample Size Determination

The sample size was not derived statistically, but empirically determined based on the safety objectives of this dose ranging trial. With N = 21 per arm (accounting for a 20% dropout rate), the rule of 3 suggests that the probability of observing at least 1 occurrence of individual AEs is at least 95% if the incidence rate is greater than 1/(N/3), which is approximately 14%.

For the plasma and CSF key secondary biomarker endpoints (CSF pTau217, plasma pTau217, and CSF tTau), the study has 90% power at a one-sided alpha of 0.1 to observe a baseline-adjusted change from baseline of 20% relative to placebo assuming a 25% standard deviation (e.g., Cohen's d of 0.8). A difference of 20% from placebo has been observed for CSF tTau and pTau with the OGA inhibitor Thiamet G in the rTg4510 tau model (Wang, Smith et al. 2018) and is a similar effect size to what has documented after 24-weeks of treatment of early AD patients with amyloid lowering therapies like lecanemab and donanemab (Salloway 2023, van Dyck, Swanson et al. 2023).

9.11 Protocol Deviations

Any deviations in the study protocol will be documented and reported in accordance with IRB requirements. No deviation from the protocol will be implemented without the prior review and approval of the IRB/IEC except where it may be necessary to eliminate an immediate hazard to a

research participant. In such case, the deviation will be reported to the IRB/IEC as soon as possible.

10 GENERAL CONSIDERATIONS: REGULATORY, ETHICAL, AND TRIAL OVERSIGHT

10.1 Regulatory and Ethical Considerations

The trial will be conducted in accordance with the consensus ethical principles derived from international guidelines including the Declaration of Helsinki, applicable ICH Good Clinical Practice (GCP) Guidelines, and applicable local laws and regulations. Should a conflict arise, the Investigator will follow whichever law or guideline affords the greater protection to the individual participant.

The protocol, protocol amendments, Informed Consent Form (ICF), IB, and other relevant documents (e.g., advertisements) must be submitted to an Institutional Review Board (IRB)/Independent Ethics Committee (IEC) by the Investigator and reviewed and approved by the IRB/IEC before the trial is initiated.

Protocol amendments require IRB/IEC approval before implementation of changes to the trial design, except for changes necessary to mitigate an immediate hazard to participants.

10.2 Committees

10.2.1 Ethics Committees

The IRB/IEC must be a properly constituted board or committee operating in accordance with 21 CFR Part 56, "Institutional Review Boards." The protocol, any protocol amendments, and the associated ICFs must be reviewed and approved by the IRB/IEC prior to screening of any potential participant. IMP may not be shipped to the Investigator until Sponsor, or its designee has received a copy of the letter or certificate of approval from the IRB/IEC for the protocol and any protocol amendments, as applicable.

All participant recruitment and/or advertising information must be submitted to the IRB/IEC and Sponsor or its designee for review and approval prior to implementation. IRB/IEC approval of any protocol amendments must be received before any of the changes outlined in the amendments are put into effect, except when the amendment has been enacted to protect participant safety. In such cases, the chair of the IRB/IEC should be notified immediately, and the amendment forwarded to the IRB/IEC for review and approval.

10.2.2 Safety Review Committee

The SRC will be formed to review safety and tolerability data and will meet on an ad hoc basis if requested by one of the members or if trial stopping rules are met as outlined in Section 7.4. The SRC will be comprised of the Sponsor's Medical Monitor, a pharmacovigilance monitor, and the trial Investigator. The SRC may, based on the nature, frequency, and/or severity of an adverse event recommend protocol modification(s), dose suspension, dose termination or study

termination. A Safety Review Committee charter will provide full guidance on the function and practices to be followed by the SRC.

10.3 Informed Consent Process

Appropriate forms for documenting written informed consent will be reviewed and approved by the Sponsor or its designee prior to investigator submission to the IRB/IEC. The Sponsor or its designee must receive a copy of the IRB/IEC's approval of the ICF before the shipment of IMP to the trial site.

The method of obtaining and documenting informed consent and the contents of the ICF will comply with ICH GCP guidelines, the requirements of 21 CFR Part 50, "Protection of Human Subjects," the Health Insurance Portability and Accountability Act (HIPAA) regulations, and all other applicable regulatory requirements.

The Investigator is responsible for obtaining written informed consent from each potential trial participant and study partner prior to the conduct of any trial procedures. The signed ICF must be retained in each participant's trial file and be accessible to the trial monitor. Participants will be given a copy of the signed ICF and will be provided with any new information during the course of the trial that might affect their continued participation in the trial.

If the protocol is amended and the ICF is revised, each participant will be required to provide written informed consent again using the revised ICF.

10.4 Data Protection

Participants will be assigned a unique identifier by the sponsor. Any participant records, datasets, or biological samples that are transferred to the Sponsor will contain the identifier only; participant names or any information which would make the participant identifiable will not be transferred. The participant will be informed that their personal study-related data will be used by the Sponsor in accordance with local data protection law. The level of disclosure must also be explained to the participant who will be required to give consent for their data to be used as described in the ICF.

The participant will be informed that their medical records may be examined by Clinical Quality Assurance auditors or other authorized personnel appointed by the Sponsor, by appropriate IRB/IEC members, and by inspectors from regulatory authorities.

10.5 Early Site Closure or Trial Termination

The Investigator will have the following responsibilities:

- Providing oversight of trial conduct at the site
- Adhering to 21 CFR, ICH guidelines, IRB/IEC requirements, European Clinical Trials Directive (if applicable), and all other applicable local regulations

- Promptly notifying the IBR/EC of significant safety findings
- Providing trial status updates to the IBR/EC as required
- Provide the Sponsor with required information to complete financial certification or disclosure statement as required by regulatory authorities.

Should the Investigator not comply with these responsibilities, the site may be closed.

The Sponsor or designee reserves the right to close a site or terminate the trial at any time. Likewise, an Investigator has the right to initiate site closure. Reasons for early site closure of a study site by Sponsor or Investigator include but are not limited to:

- Failure to follow Investigator responsibilities, as listed above
- Inadequate recruitment by the Investigator
- Discontinuation of IMP development.

Following termination or suspension, the Sponsor and Investigator will ensure the appropriate ethics committee(s) and regulatory authorities are informed, and participants are notified and transitioned, as appropriate.

11 GENERAL CONSIDERATIONS: RISK MANAGEMENT AND QUALITY ASSURANCE

11.1 Quality Tolerance Limits

Quality tolerance limits will be predefined by the Sponsor and/or its designee in a study management plan. The plan will include a description of monitoring approaches and the process for handling non-compliance with the protocol or ICH GCP guidelines.

11.2 Data Quality Assurance

Monitoring and auditing procedures developed by Sponsor and/or its designee will be implemented to ensure compliance with FDA and ICH GCP guidelines. The following principles will be set forth to ensure quality of trial data:

- The Sponsor assumes accountability for actions delegated to other individuals (e.g., Contract Research Organizations)
- The Sponsor or designee is responsible for the management of trial data including quality control
- The Sponsor (or designee) will develop a monitoring plan to detail methods, responsibilities, and requirements (including handling of noncompliance issues)
- All participant data relating to the trial will be recorded on the eCRF unless electronically transmitted directly to the Sponsor or designee (e.g., laboratory data)
- Any changes to the data will be made only by Sponsor-authorized users; changes will be captured in an electronic audit trail
- The Investigator is responsible for verifying the accuracy of data entered at the trial site
- Monitors will evaluate the site to assure the safety and rights of participants are being
 protected; and the trial is being conducted in accordance with the current protocol, trial
 agreements, ICH GCP, and all applicable regulatory requirements.

11.3 Source Data

- The Investigator will maintain accurate documentation (source data) that supports information entered in the eCRF
- The Investigator must permit trial-related monitoring, audits, IRB/IEC review, and regulatory agency inspections, and provide direct access to source data documents
- Monitors will verify source data to confirm data entered into the eCRF by authorized site personnel are accurate, complete, and verifiable

- Records and documents pertaining to the conduct of this trial (including original signed ICFs), must be retained by the Investigator for 25 years after trial completion unless local regulations or institutional policies require a longer retention period
- No records may be destroyed during the retention period without the written approval of the Sponsor.
- Written notification to the Sponsor is required prior to any transfer of records to another location or party.

11.4 Contingency Plans During Public Health Emergencies, Natural Disasters, or Other National Emergencies

If an investigational site is affected by a public health emergency, natural disaster, or other national emergency during the trial, the Sponsor will coordinate with the Investigator/Institution to ensure the safety of trial participants in accordance with GCP and available regulatory guidance documents.

The Sponsor will seek to maintain the integrity of the trial, however minimization of risk to trial participants will be considered paramount.

In such unprecedented situations, contingencies may include:

- Suspension of trial recruitment
- Alternate provisions for providing investigational product and supply chain management
- Modifications to monitoring processes and procedures.

The Sponsor will consult with Investigators and IRB/IECs in a timely manner to determine actions needed to protect active trial participants. However, changes to protect the safety of trial participants may be implemented without prior IRB/IEC approval, such as:

- Delayed administration of IMP (i.e., extended screening periods) until safety follow-up may be conducted
- Alternate methods for safety assessments (e.g., telephone, telemedicine, remote location for laboratory sample acquisition and/or processing)
- Postponement of certain visits and/or assessments deemed less critical
- Exceptions to protocol-specified visit windows.

12 APPENDIX: ADVERSE EVENTS AND SERIOUS ADVERSE EVENTS – DEFINITIONS SEVERITY AND CAUSALITY

12.1 Definitions

12.1.1 Adverse Event Associated with Study Procedures

A procedure-related AE is an AE considered by the Investigator to be related to a procedure required by the protocol (i.e., temporally associated or known risk of the procedure).

12.1.2 Adverse Event

An AE is any untoward medical occurrence associated with the use of a drug in humans, whether or not considered drug related. The term "adverse event" could include any of the following events that develop or increase in severity during the course of the trial. Examples include:

- Any sign, symptom, or physical examination finding that worsens in nature, severity, or frequency compared to baseline irrespective of association with the condition under study
- Any clinically significant laboratory abnormality or laboratory abnormality that requires medication or hospitalization
- Reactions to IMP including those occurring as a result of an overdose, abuse, withdrawal
 phenomena, sensitivity, or toxicity
- Concurrent illness
- Injury or accident.

Conditions present prior to enrollment are considered Medical History. Pre-existing conditions should be reported as a TEAE if there is a change in the frequency, intensity, or the character of the condition.

12.1.3 Serious Adverse Event

An SAE is an AE that:

- results in death
- is considered life threatening
- requires in-patient hospitalization or prolongation of existing hospitalization
- results in persistent/significant disability/incapacity
- results in a congenital anomaly/birth defect; or
- other medially important serious medical event.

12.2 Recording of Adverse Events and Serious Adverse Events

12.2.1 Severity

The intensity of each AE should be graded as mild, moderate, severe, or potentially life-threatening, using the following categories:

- Mild: asymptomatic or mild symptoms; clinical or diagnostic observations only; intervention generally not indicated
- Moderate: minimal, local, or noninvasive intervention indicated; limiting age-appropriate instrumental activities of daily living
- Severe: interrupts normal daily activities and generally requires systemic drug therapy or other treatment; usually incapacitating. May also be considered potentially lifethreatening or require urgent intervention to prevent permanent impairment, persistent disability, or death

Severity is not considered a guide for defining regulatory reporting obligations.

12.2.2 Causality

The Investigator should consult the IB when assessing relationship to IMP and consider all possible etiologies for the AE. The Investigator will assess the causality of the AE to study procedure or IMP as follows:

Attributions for "Unrelated" events:

- Unrelated: the AE is clearly not related to the IMP/procedure, beyond a reasonable doubt
- Unlikely Related: the AE is doubtfully related to the IMP/procedure

Attributions for "Related" events:

- Possibly Related: the AE may be related to the IMP/procedure
- Probably Related: the AE is likely related to the IMP/procedure
- Definitely Related: the AE is clearly related to the IMP/procedure

For the purposes of reporting to regulatory agencies, AEs deemed as Definitely, Probably or Possibly Related will be considered Related and those deemed Unrelated or Unlikely Related will be considered Unrelated.

AEs listed as related are considered to have a suspected "reasonable causal relationship" to the IMP/intervention (ICH E2A). The expression "reasonable causal relationship" is meant to convey in general that there are facts (evidence) or arguments to suggest a causal relationship.

12.2.3 Follow Up

All AEs (i.e., any new or worsening in severity or frequency of a preexisting condition) with onset after the participant signs consent for trial participation must be promptly documented on the AE eCRF via the electronic data capture system. Details of the AE must include severity, relationship to IMP, duration, and outcome.

Participants who discontinue due to treatment-emergent SAE will be monitored for safety as specified in Section 8.4.1.

Follow-up is required for all participants with AEs until the event has been resolved or the condition has stabilized. Clinically significant abnormal laboratory values should be followed until repeat tests return to normal, stabilize, or are no longer clinically significant.

12.2.4 Outcome

The outcome of an AE associated will be assessed as follows:

- Recovered/Resolved: the event has improved or recuperated
- Not recovered/Not Resolved: the event has not improved or recuperated
- Recovered/resolved with sequelae: the participant recuperated but retained pathological conditions resulting from the prior disease or injury
- Fatal: termination of life as a result of an AE
- Unknown: not known, not observed, not recorded

12.3 Reporting of Serious Adverse Events

SAEs and AESIs must be reported to the Sponsor (or designee) within 24 hours of the knowledge of the occurrence.

An SAE report will be completed as thoroughly as possible including all available details about the event and the signature of the Investigator. The SAE form will be updated when additional information is received.

A death occurring during the trial must be reported to Sponsor or its designee within 24 hours of knowledge of the death whether or not it is considered treatment related.

The Investigator also must notify the IRB/IEC of the occurrence of the SAE, in writing, as soon as is practicable and in accordance with IRB/IEC requirements and local law. A copy of this notification must be provided to the Sponsor or its designee.

12.4 Regulatory Reporting Requirements for Serious Adverse Events

Investigators are required to report any urgent safety matters to Sponsor or its designee within 24 hours. The Investigator will notify the IRBs/IECs of SAEs and urgent safety matters, in

accordance with IRB/IEC requirements and local laws and regulations. A copy of this notification must be provided to the Sponsor or its designee.

SAEs that are unexpected and considered related to the administration of the IMP will be reported by the Sponsor (or designee) to the appropriate regulatory authorities and other investigators in the form of an expedited safety report within 15 calendar days after receiving information on the SAE. The investigators will notify their reviewing IRB/IEC and other committee(s) as required by institutional policies.

12.5 Serious and Unexpected Adverse Reaction Reporting

Fatal and life-threatening suspected unexpected serious adverse reactions (SUSARs) will be submitted no later than 7-calendar days of first knowledge of the event and follow-up information submitted within an additional eight (8) days. The Sponsor will report any unexpected life threatening or fatal SAEs that are considered related to the IMP to the appropriate regulatory authorities within 7 days of receiving the information.

13 APPENDIX: DEFINITIONS AND SUPPORTING OPERATIONAL DETAILS

13.1 Contraception and Pregnancy Testing

13.1.1 Definitions Related to Childbearing Potential

Females of Childbearing Potential:

For the purpose of this document, a woman is considered of childbearing potential (WOCBP), i.e., fertile, following menarche and until becoming post-menopausal unless permanently sterile. Permanent sterilization methods include hysterectomy, bilateral salpingectomy and bilateral oophorectomy.

Note: WOCBP are excluded from participation in this trial.

A postmenopausal state is defined as no menses for 12 months without an alternative medical cause. A high follicle stimulating hormone (FSH) level in the postmenopausal range may be used to confirm a post-menopausal state in women not using hormonal contraception or hormonal replacement therapy. However, in the absence of 12 months of amenorrhea, a single FSH measurement is insufficient.

Fertile Males:

For the purpose of this document, a man is considered fertile after puberty unless permanently sterile by bilateral orchidectomy.

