1.3 Schedule of Activities

Table 1 Schedule of Activities: Screening Period

Visit:	Screening
Screening Window (Days): a,b	
Tier 1 (Prescreening Period)	From Week -12
Abbreviated (or full) informed consent (participant) ^c	X
Assign Participant Number in IWRS	X
Demographics, medical history, preliminary eligibility review ^d	X
MMSE	X
Tier 2 (Prescreening Period) ^d	From Week -12
Plasma pTau 217	X
Blood for APOE genotype	X
Tier 3 ^e (Screening Period)	Week -8 through Day -1
Full informed consent – participant & study partner	X
Inclusion/exclusion criteria review	X
CDR-SB	X
Physical examination (including neurological), height, weight	x
Prior medications	x
Vital signs	X
Electrocardiogram (triplicate)f	X
C-SSRS ^g	X
Follicle-stimulating hormone (if applicable) ^h	X
Clinical chemistry, hematology, coagulation panel, urinalysis, urine drug screen	X
Viral screen (HbsAg, hepatitis C antibody test) ⁱ	X
Tier 4 ⁱ (Screening Period)	Week -8 through Day -1
MRI ^k	(X)

AD = Alzheimer's disease; CSF = cerebrospinal fluid; C-SSRS = Columbia-Suicide Severity Rating Scale; ECG = electrocardiogram; eCRF = electronic case report form; EU = European Union; FSH = follicle-stimulating hormone; HBsAg = Hepatitis B virus surface antigen; IVDR = in vitro diagnostic regulation; IWRS = interactive web response system; MMSE = Mini-Mental State Examination; MRI = magnetic resonance imaging; PET = positron emission tomography

Consult Section 8 for guidelines on procedures and assessments. Consult the Study Reference Manual for additional information, including a recommended order of (specific) assessments for each visit.

- a The Screening Period may be up to 8 weeks in duration to allow for the completion of all screening assessments and for the evaluation of all laboratory, ECG, and imaging tests. Screening procedures will be completed over multiple days. If additional time is required, this will be considered and approved on a case-by-case basis by the Sponsor Medial Monitor.

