- e If informed consent for the full study is not obtained at Tier 1 and an abbreviated consent form was used for Tier 1 and Tier 2 screening assessments, obtain full informed consent prior to initiation any Tier 3 screening procedures.
- f ECGs should be taken supine in triplicate at approximately 1-minute intervals. Participants should rest for at least 5 minutes in the supine position before ECGs are taken.
- g The "Screen Version" questionnaire will be administered at Screening. The "Since Last Visit" questionnaire will be administered at all subsequent visits.
- h Required for females only. Females of non-childbearing potential are defined as meeting one of the following criteria: postmenopausal (defined as 12 months of spontaneous amenorrhea with other identifiable cause or 6 months of spontaneous amenorrhea with serum FSH levels > 40 mIU/mL) or 6 weeks postsurgical bilateral oophorectomy with or without hysterectomy confirmed by documentation.
- i Participants with a suspected or confirmed past history of Hepatitis C are to have hepatitis C antibody test at V1 and are excluded if the test is positive.
- j Participants may proceed to Tier 4 only after all criteria from Tier 1, 2, and 3 have been met.
- k May be scheduled earlier at the Sponsor's discretion to facilitate timely scheduling. Submit the MRI to the central MRI vendor for final determination of eligibility. Results of centrally read MRIs will be used for data analysis; results will be communicated back to the site.

Table 2 Schedule of Activities: Double-blind Intervention Period

Visit:	Day 1a, b	Day 14	Week 4	Week 8	Week 12	Week 16	Week 20	Week 24	ET°	FU ^d
										4 weeks
										(+14 days)
										post last
Visit Window (Days):	-	-4	±7	±7	±7	±7	±7	±7	±7	dose
Inclusion/exclusion criteria review	X									
Contact IWRS, randomization	X									
Physical Examination (including	X		X		X			X	X	
neurological) and Weight										
Previous/Concomitant Medications	X	X	X	X	X	X	X	X	X	X
Dispense/Review ASN51 Compliance	X		X	X	X	X	X	X	X	
Efficacy Measures										
ADAS-Cog13 ^f	X				X			X	X	
CDR-SB ^f	X				X			X	X	
MMSEf	X				X			X	X	
Safety Assessment										
Adverse Events ^g	X	X	X	X	X	X	X	X	X	X
C-SSRSh	X	X	X	X	X	Х	X	Х	X	X
Laboratory Specimens ⁱ										
Clinical chemistry, hematology	X	X	X	X	X	X	X	X	X	X
Coagulation panel j	X						X		X	
Urinalysis	X		X		X			Х	X	
Serum hormone markers	X		X		X			X	X	
Plasma for ASN51 PK ^{k,1}	X		Xk		Xk			Xk	X	

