5.4.1 Exclusion Criteria by Medical History

- Any medical or neurological/neurodegenerative condition (other than AD) that, in the
 opinion of the Investigator, might be a contributing cause to the participant's cognitive
 impairment (e.g., current history of substance abuse, uncontrolled vitamin B12 deficiency or
 abnormal thyroid function, stroke or other cerebrovascular condition, normal pressure
 hydrocephalus, Parkinson's disease, Lewy body dementia, cerebral amyloid angiopathy,
 frontotemporal dementia) or could lead to discontinuation, lack of compliance, interference
 with study assessments, or safety concerns.
- Non-amnestic presentation of AD as judged by the Investigator.
- Woman of childbearing potential (per CTFG 2020).
- Excessive alcohol use (defined as more than 3 alcoholic drinks per day or 21 drinks per week for men and 2 alcoholic drinks per day or 14 drinks per week for women) from the Screening Visit until the end of the Follow-up Period.
- History of cancer in the past 3 years. Exceptions: non-metastatic basal and/or squamous cell
 carcinoma of the skin, in situ cervical cancer, non-progressive prostate cancer, participants
 with cancer in remission > 5 years, or other cancers with low risk of recurrence or spread.
- History of human immunodeficiency virus infection (active or past), or active hepatitis C infection.
- 7. History of liver disease including hepatitis B, hepatitis C, primary biliary cholangitis, primary sclerosing cholangitis, alpha-1 antitrypsin disease, alcoholic liver disease, Wilson's disease, hemochromatosis, portal hypertension, biopsy-proven metabolic associated steatohepatitis, autoimmune hepatitis, drug induced liver disease.
- Clinically significant systemic infection or severe infection (e.g., pneumonia, septicemia) within the 30 days prior to Screening or between Screening and Day -1.
- History of seizures within 10 years prior to Screening Visit 1 or history of epilepsy (except for history of febrile seizures in childhood).
- 10. Presence of clinically significant and/or unstable psychiatric illness, in the Investigator's opinion (e.g., bipolar disorder), within the 6 months prior to Screening Visit 1 and/or a documented prior history of chronic schizophrenia.
- 11. History of major depressive disorder, bipolar disorder, or generalized anxiety disorder with an active episode in the past 5 years.

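### Table 1 footnote h accepts as non-childbearing a woman with 6 to under 12 months of amenorrhea and a raised FSH, whom Section 13.1.1 excludes as of childbearing potential

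*Combined protocol and SAP*

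**What the plan says.** Three places in the current protocol bear on whether a woman may enter.

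- **Section 1.3, Table 1, Tier 3.** The schedule lists an FSH test at Screening: "Follicle-stimulating hormone (if applicable"). Footnote h, attached to that row, defines non-childbearing potential as meeting any one of its criteria. The postmenopausal criterion is "12 months of spontaneous amenorrhea with other identifiable cause or 6 months of spontaneous amenorrhea with serum FSH levels > 40 mIU/mL". The only surgical criterion is bilateral oophorectomy, with or without hysterectomy, at 6 weeks after surgery and documented.
- **Section 13.1.1.** The definition is written for the whole document: "For the purpose of this document, a woman is considered of childbearing potential (WOCBP"), from menarche until menopause unless permanently sterile. "A postmenopausal state is defined as no menses for 12 months without an alternative medical cause". A high FSH "may be used to confirm a post-menopausal state in women not using hormonal contraception or hormonal replacement therapy", but "in the absence of 12 months of amenorrhea, a single FSH measurement is insufficient". Hysterectomy, bilateral salpingectomy and bilateral oophorectomy all count as permanent sterilization. The section adds: "Note: WOCBP are excluded from participation in this trial".
- **Section 5.4.1, exclusion 3.** The operative criterion is "Woman of childbearing potential (per CTFG 2020"). The synopsis repeats it. Neither copy refers to footnote h or to Section 13.1.1.

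**The concern.** Eligibility on this point depends on which definition the site reads. Footnote h sits where staff order and interpret the FSH, and it is worded as a definition, not as a summary of one given elsewhere. A site could follow it in good faith and enroll a woman whom Section 13.1.1 excludes.

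The protocol relies on excluding every woman of childbearing potential. Section 13.1.3 marks pregnancy testing as not applicable, criterion 11 in Section 5.3 asks for contraception only from men with partners of childbearing potential, and Table 7 lists only partner pregnancy. A woman misclassified at screening would meet no later check in the visible text.

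**Working it through.** No sample size, power or alpha figure is involved. The check is to put the same women through both definitions.

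| Woman | Table 1 footnote h | Section 13.1.1 | Agree? |
|---|---|---|---|
| Not sterilized, 12 months or more without menses, no other cause | Non-childbearing (reading *with* as *without*; see below) | Postmenopausal, not excluded | Yes |
| Not sterilized, 6 to under 12 months, one FSH above 40 mIU/mL | Non-childbearing | Childbearing potential, excluded | **No** |
| Not sterilized, 6 to under 12 months, FSH 40 mIU/mL or below | Not met | Childbearing potential, excluded | Yes |
| Not sterilized, under 6 months, any FSH | Not met | Childbearing potential, excluded | Yes |
| Bilateral oophorectomy, 6 weeks or more ago, documented | Non-childbearing | Permanently sterile, not excluded | Yes |
| Hysterectomy alone or bilateral salpingectomy alone | Not met by the surgical route | Permanently sterile, not excluded | **No** (opposite direction) |

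1. The second row is the main conflict. Footnote h accepts any one of its criteria, so the 6-month route is enough by itself. Section 13.1.1 has no FSH alternative to the 12 months; it allows FSH only as confirmation.
2. The 6-month route rests on one measurement as scheduled. FSH appears once, at Screening in Table 1, and in neither Table 2 nor Table 3. That is the single test which Section 13.1.1 calls insufficient.
3. Footnote h does not carry over the restriction of FSH confirmation to women not taking hormonal contraception or hormone replacement.
4. The last row is a second, milder mismatch. Footnote h recognises fewer operations than Section 13.1.1, but adds a 6-week interval and documentation that Section 13.1.1 lacks. Here footnote h is the stricter text.
5. Read literally, the 12-month arm of footnote h requires amenorrhea *with* another identifiable cause, the reverse of the Section 13.1.1 condition. This is very likely a slip for *without*, and the same edit corrects it.
6. The age range starts at 50 (Section 5.3), so a woman in the second row can be screened. About 78 participants of both sexes are planned. The documents give neither the number of women nor the number with 6 to under 12 months of amenorrhea.

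**The case against.** The strongest reply is that Section 13.1.1 plainly governs. It is written for the whole document, Section 5.6 judges eligibility against Sections 5.3 and 5.4 and bars waivers, and exclusion 3 names an authority. Section 5.2 strongly encourages sites to discuss eligibility questions with the Medical Monitor. This lowers the chance of error, and Section 13.1.1 does have the better claim. It does not settle the matter. The named authority is an outside guideline whose content the protocol does not reproduce at exclusion 3, the criterion does not send the site to Section 13.1.1, and a no-waiver rule does not stop a site that believes the criterion is met.

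A second reply is that footnote h speaks of FSH levels, so repeat tests might be intended. The body of the laboratory table (Table 8) is not shown, so an instruction there cannot be ruled out. But the visible schedules contain only the Screening test, and even repeated FSH would not meet the 12-month definition.

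A reader might go further and infer that the absence of pregnancy testing and female contraception is a separate defect. The documents do not support that: both follow from excluding all women of childbearing potential. Section 8.5.1, on participants who become pregnant, is listed in the contents but its body is not shown, so the point is limited to the absence of a visible safeguard.

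A reader might also try to size the problem by counting weeks of dosing or PET scans until a woman reaches 12 months. Such a count must assume that amenorrhea continues, whereas the risk is that menses or ovulation resume. Table 2 also schedules a PET scan at Early Termination as well as at Day 1 and Week 24, so the number of scans is not fixed. These counts would measure neither likelihood nor harm.

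**Conclusion.** The inconsistency is real. For a non-sterilized woman with 6 to under 12 months of spontaneous amenorrhea and one screening FSH above 40 mIU/mL, two current parts of the protocol give opposite eligibility results, and the criterion itself does not say which applies. Confidence is high in the mismatch of the texts and lower in the prediction that a site would act on footnote h.

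The size is small: few women, possibly none. It would be an overstatement to say that ineligible women will be enrolled, or that serious fetal harm is likely. The visible text gives no reproductive-toxicity information, and the risk summary and the radioligand section are not shown, so the harm is left ungraded. Sample size, power and error rates are unaffected. The correction is still worth making, because screening is the only visible control and the change is cheap.

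The conclusion rests on Section 13.1.1 as written and on the visible schedules. The content of the guideline cited in exclusion 3 was not used.

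**What to change.** - **Footnote h, postmenopausal route.** Delete the 6-month FSH alternative. Require 12 months without menses and without an alternative medical cause, which also corrects the *with*/*without* slip. Keep FSH as confirmation only, in women not using hormonal contraception or hormone replacement.
- **Footnote h, surgical route.** Align it explicitly with Section 13.1.1 by listing hysterectomy, bilateral salpingectomy and bilateral oophorectomy. Keep the documentation and 6-week conditions.
- **Exclusion 3 in Section 5.4.1 and its synopsis copy.** Add a reference to Section 13.1.1 as the definition to apply, keeping the guideline citation as its source.

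The cost is one rewritten footnote and two cross-references, with no change to procedures or endpoints. There are two consequences to accept openly. A few perimenopausal women must wait until 12 months of amenorrhea and then be considered for rescreening, which Section 5.6 allows on a change in status in consultation with the Medical Monitor. Footnote h would also newly recognise hysterectomy or bilateral salpingectomy alone. That widens the footnote, but only to what Section 13.1.1 already accepts.
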